8 PRAGMATIC TRIAL OVERSIGHT

8.1 *Data Safety Monitoring by Safety Officer*

[name] will act as the Safety Officer for the Phase 3 pragmatic trial.

The Safety Officer and PI will advise NIA of its findings and reports will be shared with the KPWHRI IRB, as required. We will be responsive to additional specific requests for data reports that may be requested by the Safety Officer or NIA program staff.

Confidentiality will be maintained during all phases of review and deliberations.

A separate data safety monitoring plan accompanies this protocol.

9 QUALITY CONTROL AND QUALITY ASSURANCE

9.1 *Study Procedures*

Standard operating procedures for the study will be detailed in the Manual of Procedures. An overview of procedures is provided in this protocol.

9.2 *Protocol Deviations*

Staff will immediately report protocol deviations to the Project Manager, who will inform the PI. Any deviations will be considered noncompliance with this protocol or Good Clinical Practice. Protocol deviations will include privacy breaches, and IT-related problems that lead to errors in protocol adherence.

Protocol deviations that may impact patient safety or study data integrity will be immediately reported to the PI and PM. The Safety Officer will be informed within 5 business days of study staff becoming aware of a protocol deviation impacting patient safety or study data integrity.

Staff will report all other protocol deviations. The KPWHRI IRB will be notified of deviations per reporting requirements. The NIA program director and Safety Officer will review protocol deviations in the regular data reports.

Events not considered protocol deviations: Due to the pragmatic aspects of the study, the failure of a provider or patient to adhere to the protocol (e.g., not responding to request for information on a patient, not completing training), are not considered protocol deviations. These uncontrolled and expected events are of scientific interest due to the pragmatic nature of the study.

10 ETHICS/PROTECTION OF HUMAN SUBJECTS

10.1 *Ethical Standard*

The investigator will ensure that this research study is conducted in full conformity with the principles set forth in The Belmont Report: Ethical Principles and Guidelines for the Protection of Human Subjects of Research, as drafted by the US National Commission for the Protection of Human Subjects of Biomedical and Behavioral Research (April 18, 1979) and codified in 45 CFR Part 46 and/or the ICH E6.

10.2 *Potential Risks and Benefits*

None of the individual interventional components of this study are experimental in nature. All components have been tested and demonstrated effective elsewhere. No medications or other treatments are withheld or delayed. Prescribers are not advised to stop antipsychotic medications and remain free to exercise their own clinical judgment.

10.2.1 *Potential Risks*

One component of the skills training is to brainstorm strategies for reducing problem behaviors. For example, PLWD may become oppositional/defiant when asked to get dressed or bathe. This brainstorming process involves some trial-and-error and it is possible that caregivers, with the best of intentions, may make problem behaviors temporarily worse as they experiment with their personalized strategies (A-B-C problem solving plan). This experience may be distressing and/or frustrating for both caregiver and PLWD.

10.2.2 *Potential Benefits*

There is potential for improvement in mental health and quality of life of the caregiver due to practicing the skills taught as part of the intervention and coaching received. The skills are designed to reduce interpersonal conflict between caregiver and PLWD as well as to increase participation in pleasant activities.

It is anticipated that this research will yield important new information regarding alternatives to antipsychotic medication use in persons with dementia. The results of this study will also serve to give doctors and caregivers of this population with more effective tools for managing troublesome and stressful behavior problems in this group of patients

10.3 *Institutional Review Board*

The protocol and project materials for providers and patients and caregivers have been submitted to the KPWHR IRB and approved. Amendments require review and approval by the IRB before the changes are implemented.

10.4 *Subject Confidentiality*

Appropriate steps will be taken to safeguard participant confidentiality. This includes the following:

- All project data will be maintained on secure, password protected servers at clinical sites. Only project staff needing this information for their work will have access. Members of the study team include Epic programmers from the delivery system;
- Participants will be identified using only subject ID in any study analytic database(s) at each site;
- The protocol, documentation, data and all other identifying information will be held in strict confidence. No information about the project will be released without prior approval of NIA. Authorized representatives of the NIA may inspect records, as needed.

10.5 *Future Use of Identifiable Data*

Identifiable information will be destroyed within 5 years of the end of the study, consistent with funding, HIPAA and IRB requirements.

We have no plans to retain identifiable information beyond this period. If this plan changes, we will obtain appropriate IRB approval.

11 DATA HANDLING AND RECORD KEEPING

11.1 *Data Management Responsibilities*

Both institutional and application level access granted by the local information security office and simultaneous knowledge of both a valid username and password are required to access data collected in electronic records. Any paper records generated with patient identifying information will be kept in locked filing cabinets in secured office buildings.

No participant data shall be overwritten by project staff. As necessary, variables may be recoded into new variables for analyses, so as to preserve the original record. All changes will be documented.

Final datasets will be saved electronically, clearly labeled and stored in a secure project folder on the KPWHRI server accessible only to project staff.

11.2 *Data Capture Methods*

The majority of data for this pragmatic study is captured electronically in REDCap, including study enrollment, note taking by coaches, and collection of baseline and outcome measures. All information entered into the REDCap questionnaires by participants is stored behind the KPWRHI firewall.

Cost and utilization data will be collected from the KPWHRI virtual data warehouse.

All electronic records will be kept in a 21 CFR Part-11 compliant data capture system, which includes password protection.

11.3 *Study Records Retention*

Identifying information and linking files will be destroyed within 5 years of the conclusion of the project unless consent to retain these files is granted by the IRB. Following this time, no other records will be destroyed without the consent of NIA. It is the responsibility of NIA to inform the investigator when these documents no longer need to be retained.

12 DATA SHARING PLAN

Data and resource sharing are an integral part of the STAR-VTF research program.

12.1 *Data Sharing Experience*

We at KPWHR have a long history of sharing data with investigators locally and at other institutions and strongly support NIA's effort to promote data sharing of results of publicly funded research to scientists in the US and elsewhere, with due respect for confidentiality and privacy. Our success supporting these projects is built on the understanding that effective data sharing means providing more than just data – it means offering programmatic and scientific support through an iterative process tailored to the needs of our external collaborators to help them understand and appropriately interpret data. Our data sharing philosophy ensures the highest quality science while safeguarding the protection of data on STAR-VTF participants.

12.2 *Data and Resource Sharing Plan*

Completely de-identified datasets will be available for download. These will be based on published STAR-VTF papers and include documentation needed to ensure reproducibility. These data sets will be easily accessible with clear documentation of included variables. Custom datasets will be available upon request from the STAR-VTF team to support ancillary studies, collaborative meta-analyses, and external studies.

Below we describe how we meet the five elements of NIA's Guidance on Data Sharing.(25)

12.2.1 *Access - STAR-VTF Repository and Data Sharing Capacity*

We will make completely de-identified study data available on the National Archive of Computerized Data on Aging (NACDA)(26) following the Guide to Social Science Data Preparation and Archiving(27). We will transform SAS files into comma delimited text files so that the data can be used in a variety of statistical software packages.

Each participant will have a unique study identification number linking tables for demographic data, item and total scores for standardized instruments, healthcare utilization, and pharmacy utilization. All dates will be transformed to “days relative to randomization”. Cost data will be standardized to the Medicare fee-for-service fee schedule to protect financial data.

We will also publish a data dictionary providing metadata descriptions in accompanying excel and pdf formats. Each variable will have a unique name, English language description, and description of its type (string, numeric) and length.

12.2.2 Timetable for Data Release

We will make the study data available prior to the online publication of the primary outcomes manuscript.

12.2.3 Restrictions to Data Sharing

We do not share data in any manner that may be deemed commercial or seen as selling data. Prior to downloading data, investigators will be required to make written application for our approval. Such approval shall not be unreasonably withheld provided the data will be used for public interest research or for the purposes of validating our reported findings.

Clinical notes that interventionists use to coach study participants will not be included in the publicly available data.

12.2.4 Data Deidentification Procedures

Respecting privacy and minimizing risk of identifiable information disclosure of participants is of utmost importance. We have well-developed internal policies and procedures in place to make sure that confidentiality is maintained. We will build on KPHRI's existing secure data architecture and management systems to accommodate new data. When data are transferred NACDA, the PI will work closely with the Director of Data Programming and IT and the KPHRI IRB to ensure data are protected to be compliant with HIPAA and IRB requirements. Prior to transfer from KPHRI, a dedicated programmer and biostatistician pair with knowledge of the data will pre-review files to ensure compliance with regulations, alignment of data elements with permissions, and use of strategies to mitigate re-identification risk. Structured data extracted from source data will be transferred as either comma delimited text or SAS files.

Unique identification numbers are assigned to all participants. Only the PI and designated programmer will have access to the participant's actual identification on an as-needed basis. All data collected for analytic purposes will be filed separately from clinical information, which may include participant names. Participant privacy and confidentiality will be protected through the creation of limited data sets and, where possible, data sets that are de-identified in accordance with the HIPAA Privacy Rule. Data will be transferred via KPHRI's web-based secure file transfer (SFT) application, which uses the 128-bit Secure Sockets Layer encryption protocol, the standard for secure Internet information transfer, and meets the 2009 HIPAA HITECH safe harbor standard. Data will be maintained locally in password protected files located in a secure server with restricted access.

Within KPHRI, only authorized project staff can access identifiable data. EHR data from KPWA systems and research data from other Cores will be stored in the KPWA Data Warehouse with unique anonymous encrypted identifiers that cannot be linked to KPWA identifiers without specific programming. Data handling procedures will be clearly documented and comply with KPWA guidelines for data storage, transfer, and destruction.

12.2.5 Data Curation and Documentation

We will employ robust quality processes to identify and correct errors for STAR-VTF Repository elements. Structured data from the KPWHRI virtual data warehouse, captured as electronic health record (EHR) data from KPWHRI's instance of Clarity, or study data collected via REDCap will undergo comprehensive quality assurance to: (1) confirm that values fall within valid ranges and are internally consistent with related variables; (2) quantify levels of missing responses, accounting for complex skip patterns when relevant; and, (3) visualize temporal patterns in data elements to uncover unexpected trends, for instance from ICD-10 coding changes. Data quality concerns will be investigated fully by the study programmer and biostatistician in partnership with the PI and project manager. Corrective actions will be taken, and data rechecked to confirm issue resolution before certification.

Once clean structured data elements are procured for each data domain, the programmer and biostatistician pair will collaborate with the PI and project manager to derive, validate, and provide detailed documentation of analytic variables relevant to address all project aims. Documentation in each case will include an exhaustive, user-friendly data dictionary that describes variable definitions, coding, construction, and usage. This documentation will guide all potential users in efficiently and appropriately using the data for analysis and sharing.

Data files will be accompanied by statistical summaries of key features of the data and a curated suite of SAS programs that can be used and adapted to produce other potential summaries of interest or to generate different types of analysis-ready files. These summaries and documentation of variables and linked datasets will be available on the NACDA website. This process ensures that accessible and easy-to-use data can be leveraged to produce transparent and reproducible analyses with the most up-to-date and quality-controlled information available.

12.3 Data Sharing Summary

In summary, we agree with the NIA that the best means to maximize the value of investments made in this study is to share the data as widely as possible. We are thoroughly committed to data sharing, are proud of our accomplishments to date in this area and look forward to continuing to broadly collaborate and share KPWHRI data and resources under the STAR-VTF project.

STAR Caregivers – Virtual Training and Follow-up

Grant Number: 1 R01AG061926-01

Principal Investigator: [name]

STATISTICAL ANALYSIS PLAN

Background/overview/purpose of study:

This is a randomized trial that tests whether receipt of telehealth training for caregivers of people with dementia can reduce utilization of antipsychotic medications, as well as improve the living conditions of both the caregiver as well as the person with dementia.

Scientific questions and outcomes:

1. Is there a change in the rate of antipsychotic medication fills within eight weeks, comparing the intervention to the control arm
 - a. Main measures: Any fill within eight weeks (binary), any refill within eight weeks (binary)
2. Is there a change in standardized scales of caregiver mastery as well as dementia symptoms.
 - a. Primary scales: Revised Memory Problem and Behavior Checklist, Caregiver Mastery, Kingston Caregiver Stress
 - b. Secondary analyses: Dementia Severity Rating Scale subscales

Predictors of interest (independent variable, could be just treatment groups, indicate type as in outcome of interest section):

All analyses will adjust for gender and age, as well as the baseline score. (e.g. the caregiver mastery analysis will adjust for caregiver mastery at baseline) Our variable of interest will be the randomization group.

Unit of analysis:

The dyad of the caregiver and person with dementia.

Other data/analytic specifics (e.g. subgroups of interest, brief discussion of missing data):

Subgroups will be exploratory analyses; we are not specifically powered on any. Missing data will be accounted for via multiple imputation via chained equations, using 100 imputed datasets.

Analytic approach, special Issues and proposed sensitivity analyses:

This is a straightforward randomized trial, so analyses will be run using ordinary least squares regression with empirical standard errors for continuous outcomes, and logistic regression for binomial outcomes. Rubin's Rules will be used to combine results across the multiple imputation datasets.

Analytic software (and version if known):

Stata, version 17.0

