AIM 3: Test the hypotheses that (H1) caregiver participants in STAR-VTF will have lower levels of caregiver burden at 8 weeks and 6 months compared to an attention control group; and (H2) PLWD participants in STAR-VTF will have lower rates of antipsychotic medication use at 6 months compared to control. Secondary outcomes are: caregiver depression, caregiver stress and caregiver self-efficacy. We propose to recruit 100 CG-PLWD dyads (50 per arm).

This will be the first study to test a low intensity, self-directed caregiver training program with remote support from social workers. It will also be the first study to measure changes in antipsychotic medication use by PLWD after CG training. Kaiser Permanente is an ideal setting because we have access to the complete EHR, prescription medication use, health care use, and demographic data. We will be able to identify and enroll participants in real-time using an automated data algorithm as we have done previously.(22) This study will be an important step in expanding access to training and support in a format that could be implemented within integrated delivery systems with capitated payments (i.e., Accountable Care Organizations). Growing use of EHR portals in these organizations will further increase demand for web-based care management/support. Demand will also increase as today's near-retirees, familiar with web-based applications, develop ADRD. Kaiser Permanente has pioneered such efforts and is the lead site in the Mental Health Research Network (MHRN). Findings from this study will inform a future multi-site pragmatic trial across the 13 health systems and 12 million enrollees in the MHRN.

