3.2 Secondary Outcomes

The following secondary outcome measures for the trial will be assessed:

- (1) **Antipsychotic medication Use.** Proportion of participants will at least one antipsychotic prescription refill after initial medication dispensing, using automated system pharmacy data.
- (2) **Change in caregiver depression.** Self-reported caregiver depression assessed by the 8-item Patient Health Questionnaire (PHQ-8). The PHQ-8 is an eight-item measure of depression that assesses symptoms over the last two weeks. The total sum of the 8 responses from the PHQ-8 ranges between 0 and 24 with higher scores indicating worse outcome. In general, a total of 10 or above is suggestive of the presence of depression.
- (3) **Change in caregiver self-efficacy.** Self-reported caregiver self-efficacy assessed by the Caregiver Mastery Scale. Total scores can range from 7 to 35, with higher scores reflecting greater caregiver mastery. The Caregiver Mastery Scale is a 7-item measure of self-efficacy. is a 7-item self-report scale, indicating the extent to which respondents agree (5) or disagree (1) with each item. Three items with negative statements are reverse-scored. Total scores can range from 7 to 35, with higher scores reflecting greater caregiver mastery.
- (4) **Change in caregiver stress.** Caregiver stress will be measured on the Kingston Caregiver Stress Scale. This is a 10-item measure with respondents rating the level of stress between 1 (coping fine, no stress) to 5 (extreme stress, feeling at the end of rope). Total scores vary between 10 and 50.
- (5) **Response rates for baseline, 8-week, and 6-month measures.** We will assess participants' willingness to complete study measures using the REDCap online survey by the proportion completing study measures at each time point.
- (6) **Training Completion rate.** We will report training completion rates as a measure of feasibility. Completion will be defined as viewing all 6 online training modules, conducting at least 3 phone calls with a study coach and sending at least one secure message to a study coach in the baseline to 8-week period and one message in weeks 9 through 24.
- (7) **Primary care visit rates.** Measured as the number of primary care visits per eligible study participant during the study period.

- (8) **Urgent care visit rates.** Measured as the number of urgent care visits per eligible study participant during the study period.

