5 STUDY ENROLLMENT AND WITHDRAWAL

5.1 *Inclusion and Exclusion Criteria for Persons Living with Dementia*

The investigators will identify and recruit PLWD-CG dyads in which the PLWD has filled a new prescription for an antipsychotic medication. The study programmer will identify potential PLWD-CG dyads using an automated data algorithm that queries claims data and electronic health record (EHR) data on a weekly basis.

Because we will enroll dyads, there are inclusion/exclusion criteria for both persons living with dementia and their caregivers.

Persons with dementia inclusion criteria:

- Aged \geq 65 years
- Diagnosis of Alzheimer's Disease or related dementia (ADRD)
- Expected to live \geq 6 months from enrollment

Persons with dementia exclusion criteria:

- A diagnosis of bipolar disorder or schizopreniform disorder
- The primary care physician's opinion is that the person with dementia is expected to live less than 6 months.
- Primary language is not English (patient requires a translator).

5.2 *Inclusion and Exclusion Criteria for Caregiver Subjects*

Potentially eligible caregivers are identified by the family contact information in the electronic medical record.

Caregiver inclusion criteria:

- Aged \geq 21 years
- Lives with person with dementia or within 8 miles
- Provides at least 8 hours of care per week

Caregiver exclusion criteria:

- Diagnosis of Alzheimer's Disease or related disorders.
- Caregiver is not the spouse or adult child of the person living with dementia
- Primary language is not English (caregiver requires a translator).

5.3 ***Randomization Assignment Procedures***

5.3.1 ***Randomization Procedures***

The study biostatistician will create a randomization schedule and this will be uploaded into a REDCap database. Caregivers who remain eligible for the study after screening will be randomized within REDCap following the pre-set randomization schedule. All eligible caregiver-patient dyads will be block randomized to ensure comparable numbers of dyads enrolled in each study arm. Caregivers will be categorized according to age (<75 years, >=75 years), sex, and spouse/non-spouse.

R, an open-source statistical computing software, will be used to generate an even number of control and intervention assignments within each block.

5.3.2 ***Blinding***

Study staff will be blinded to study arm when verifying subject eligibility.

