 - Do you believe [PLWD] will live at least 6 months from today? [YES/NO]

- Was [antipsychotic medication] prescribed for behavioral/psychological symptoms of dementia? [YES/NO]
- Is there any other reason to NOT invite this patient and family caregiver to be in the research study? [YES/NO]

Recruitment will not proceed without a response to these questions by the prescribing clinician.

In the third stage, a study staff person will mail an invitation letter to the PLWD-CG dyad. This is followed by a screening phone call approximately 3 business days later. The purpose of the screening call is to determine:

- Willingness to take part in the study regardless of the randomization group.
- Ability to read and speak English.
- Determine whether the CG has ever been diagnosed with Alzheimer's disease or related dementia
- Confirm the PLWD does not live in an adult family home, assisted living facility, skilled nursing facility, or memory facility.
- Whether the caregiver is 21 years or older.
- Whether the caregiver lives in the same household as the PLWD or within 8 miles (30 minutes).
- Whether the caregiver spends at least 8 hours providing care to the PLWD
- Whether the caregiver is the DPOA and if not who that person is.
- Whether the caregiver is the spouse or adult child of the PLWD
- Caregiver access to a computer or other device where the caregiver can access the patient portal, personal email and websites to complete the online training.
- Whether the caregiver uses MyChart – the Kaiser Permanente patient portal - to email the doctors that care for the PLWD
- Administer the Short Portable Mental Status Questionnaire to the caregiver.

If the PLWD-CG dyad remains eligible after the 3-step verification process then a study staff person will randomize the dyad in REDCap and schedule an orientation telephone visit.

If the caregiver is not the DPOA and the PLWD is unable to consent, the study staff person will request the contact information of the person who is DPOA. If the dyad is otherwise eligible, the DPOA will be contacted to obtain verbal consent on behalf of the PLWD.

6.3 *Consent*

6.3.1 *Verbal Consent for screening questions*

Following the recruitment packet mailing, two things may happen:

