7.2.2 Aim 1. Feasibility/Acceptability

We will measure response rates for follow-up data collection using the online survey functionality in REDCap. We will use descriptive statistics to characterize response rates by study arm and demographic characteristics. We will use generalized estimating equations (GEE) with a working correlation matrix to estimate a logistic regression model for response vs. non-response. We will estimate separate models for the 8-week and 24-week outcome periods. Models will be adjusted for PLWD stage of dementia (DSRS), PLWD FAQ score, PLWD age and sex, caregiver relationship (spouse, non-spouse), caregiver age and sex, caregiver highest level of education attained, PLWD residential status (living with caregiver full-time versus not) and study arm.

7.2.3 Feasibility/Acceptability - Completion of Training.

We will use descriptive statistics to characterize completion rates by study arm and demographic characteristics. We will use generalized estimating equations (GEE) with a working correlation matrix to estimate a logistic regression model for completion vs. non-completion. Models will be adjusted for PLWD stage of dementia (DSRS), PLWD FAQ score, PLWD age and sex, caregiver relationship (spouse, non-spouse), caregiver age and sex, and caregiver highest level of education attained, and study arm.

7.2.4 Assess the feasibility and acceptability from the payer perspective.

We will use descriptive statistics to characterize the effort required by coaches to facilitate caregiver training. These measures are (1) time reading secure messages, (2) number of exchanges per message thread, (3) number of ad hoc phone calls required (i.e., other than the 6 scheduled calls).

7.2.5 Primary Care, Urgent Care and Emergency Department Use.

We will use longitudinal, generalized estimating equations (GEE) to estimate a Poisson regression model for adjusted mean monthly visit rates (separately by visit type) in the STAR-VTF arm compared to the attention control arm in the 6 months following randomization. Models will be adjusted for PLWD stage of dementia (DSRS), PLWD FAQ score, PLWD age and sex, caregiver relationship (spouse, non-spouse), caregiver age and sex, and caregiver highest level of education attained, and study arm. We will use the robust sandwich estimator to calculate standard errors to account for repeated (i.e. 6 monthly) observations within people and the misspecified variance in the Poisson model.

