7.2.6 Effect of STAR-VTF on CG burden and PLWD antipsychotic medication use.

We will measure overall caregiver burden using the Revised Memory and Problem Behavior Checklist (RMPBC). We will use GEE with a working correlation matrix to estimate the regression model, using robust sandwich estimators to calculate standard errors accounting for within person correlation. We will adjust for baseline pre-randomization covariates: PLWD stage of dementia (DSRS), PLWD FAQ score, PLWD age and sex, caregiver relationship (spouse, non-spouse), caregiver age and sex, and caregiver highest level of education attained.

We will use generalized estimating equations (GEE) with a working correlation matrix to estimate a logistic regression model for refill (versus no refill) of the initial antipsychotic medication. Models will be adjusted for PLWD stage of dementia (DSRS), PLWD FAQ score, PLWD age and sex, caregiver relationship (spouse, non-spouse), caregiver age and sex, and caregiver highest level of education attained, study arm. We will again use GEE with a working correlation matrix to estimate a logistic regression model for daily versus “less than daily” use of antipsychotic medication (as reported to the coach). Models will again be adjusted for pre-randomization variables listed above.

7.2.7 Caregiver depression, stress and self-efficacy.

Caregiver depression will be measured using the PHQ-8. Caregiver self-efficacy will be measured using the Caregiver Mastery Scale. Caregiver stress will be measured using the Kingston Caregiver Stress Scale. We will again use GEE to compare the mean PHQ-8, CMS and Kingston scores in the STAR-VTF and attention control arms. Models will be adjusted for pre-randomization variables as above.

7.3 *Handling of Missing Data*

Preventing missing data is superior to statistical treatment. We will make every effort to collect data on all study participants. If there are substantial missing data or significant loss-to-follow-up, we will use inverse probability weighting(23) to rebalance the STAR-VTF and attention control group. Inverse probability weights are used to rebalance groups on prognostic factors when the treatment and control groups become unbalanced over time, post-randomization, due to study drop out. If we find intermittent missing data, we will instead use multiple imputation(24) via chained equations to address the problem, using at least 10 imputed datasets and combining results using Rubin's rules.

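### The protocol counts antipsychotic refills from a dispensing that precedes randomization, and the SAP gives its eight-week fill and refill measures no start date

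*SAP*

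**What the plan says.** Protocol 5.1 recruits dyads in which "the PLWD has filled a new prescription for an antipsychotic medication". Under 6.2, randomization comes only after a weekly data pull, a chart review, a mandatory reply from the prescriber, a mailed invitation and a screening call. Of the call, 6.2 says: "This is followed by a screening phone call approximately 3 business days later". Where the caregiver does not hold decision-making authority for a person unable to consent, 6.3.3 also places the representative's consent before randomization.

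Protocol 3.2(1) defines the antipsychotic outcome as the proportion with "at least one antipsychotic prescription refill after initial medication dispensing", taken from pharmacy data. Section 7.2.6 models "refill (versus no refill) of the initial antipsychotic medication". Neither limits the count to events after randomization. By contrast, 7.2.5 counts visits "in the 6 months following randomization".

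Hypothesis H2, in Aim 3 of section 2.2, is that "PLWD participants in STAR-VTF will have lower rates of antipsychotic medication use at 6 months compared to control". The SAP's first scientific question compares antipsychotic fills between arms, with "Main measures: Any fill within eight weeks (binary), any refill within eight weeks (binary"). It does not say what the eight weeks are measured from, whether the index fill is excluded, or how a fill differs from a refill.

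**The concern.** An outcome in a randomized comparison should consist of events that assignment could have influenced. The protocol's refill clock starts at the initial dispensing, which is the recruitment trigger and so precedes randomization in every dyad. A person who refills while eligibility is being confirmed has met the outcome before an arm exists, and nothing the program does can change that. Each such person is a fixed event in whichever arm they later join.

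The SAP leaves the starting point open. One choice makes one of its two measures uninformative, and an undefined start lets the analyst settle the definition after the data are in hand. At stake is the interpretation of H2: a null result on antipsychotic use could not be separated from dilution by events that were already fixed.

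**Working it through.** **The plan's own figure.** Section 7.1.1 powers the RMBPC only: d = 0.65, type-I error 0.05, power 80%, 39 per arm. A two-sided two-sample t-test gives 38.14, rounded up to 39, so the figure reproduces. Inflating by 30% gives 39 × 1.30 = 50.7, against a stated target of 50. No power is stated for any antipsychotic measure. All that carries over is the 50 per arm, which is reasonable here because 5.4 keeps measuring antipsychotic use after a caregiver withdraws.

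**Order of events.** Index fill → weekly list → chart review → prescriber reply → mailed letter → screening call → representative's consent where needed → randomization. The only intervals the documents give are the weekly pull and about 3 business days from letter to call. The prescriber's reply has no time limit. The gap is therefore real, but its length is unknown.

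**What each possible starting point implies.**

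- Window starts at the index fill: any fill is 100% v 100%, the difference is 0, and a logistic model cannot estimate an arm effect. Any refill includes refills made during recruitment.
- Window starts at randomization: the index fill and earlier refills drop out of both measures. Any later fill of the initial drug is a refill, so the two measures differ only through switches to another antipsychotic, provided refill means the initial drug, as in 7.2.6.

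**Dilution under the protocol's wording.** Let q be the share in each arm who refilled before randomization, and p the refill rate after randomization. The counted rate is q + (1 − q)p, so the risk difference is (1 − q) times the undiluted one. Power uses the pooled-variance two-proportion test, two-sided 0.05, n = 50 per arm:

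power = Φ[(d − 1.96·SE0)/SE1], where SE0 = √(2p̄(1 − p̄)/n), SE1 = √([p1(1 − p1) + p2(1 − p2)]/n), d = p1 − p2 and p̄ is the mean of p1 and p2.

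For 70% v 42% and q = 0: d = 0.28, SE0 = 0.0993, SE1 = 0.0952, power 81.5%. For q = 0.2: rates 0.760 v 0.536, d = 0.224, SE0 = 0.0955, SE1 = 0.0929, power 65.4%.

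| q (assumed) | 70% v 42%: counted rates | power | 60% v 35%: counted rates | power |
|---|---|---|---|---|
| 0 | 70.0 v 42.0 | 81.5% | 60.0 v 35.0 | 71% |
| 0.1 | 73.0 v 47.8 | 73.8% | 64.0 v 41.5 | 62% |
| 0.2 | 76.0 v 53.6 | 65.4% | 68.0 v 48.0 | 53% |
| 0.3 | 79.0 v 59.4 | 56.6% | 72.0 v 54.5 | 44% |

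Both pairs of rates and every q are assumptions.

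**Sensitivity to who the early refillers are.** The q = 0 row is what the fix would recover only if early refillers later behave like everyone else. Suppose instead that they are persistent users who refill after randomization at 95% v 90% (an assumption), with q = 0.2 and 70% v 42% in the rest. Control: 0.2 × 0.95 + 0.8 × 0.70 = 0.750. Intervention: 0.2 × 0.90 + 0.8 × 0.42 = 0.516. Power with the fix is 68.5%, against 65.4% without it: a gain of about 3 points rather than 16.

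**The case against.** The strongest reply is that the SAP's eight weeks most naturally run from randomization. Other periods in the protocol do: the control-arm messages in 5.5, visit rates in 7.2.5 and the shared-data dates in 12.2.1. On that reading the index fill and earlier refills fall outside both SAP measures. This stands as far as it goes. A reader might infer that the index fill already satisfies the SAP's any-fill measure, but the SAP does not say so; its defect is an undefined start, not a stated inclusion. The reply does not reach protocol 3.2(1), which names its starting point, and that point precedes randomization.

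A reader might also infer that one of the two SAP measures must be either constant or redundant. The documents do not establish that. Section 7.2.6 ties refill to the initial drug, so someone switched to another antipsychotic would have a fill but no refill. How often that happens is unknown.

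It is also fair to say that the trial remains valid without the change. The outcome is secondary in the protocol, and 7.2.6 separately models daily v less-than-daily use as reported to the coach, which this point does not touch. Nor did the plan promise 80% power for this outcome; with 60% v 35% it would have 71% even with no dilution.

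**Conclusion.** The point holds for the protocol as written and, as an ambiguity, for the SAP. Following 3.2(1) literally counts refills made before assignment and shrinks the H2 risk difference by the factor (1 − q).

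A reader might take this as bias for or against the program. The documents do not support that: the events precede assignment and are balanced between arms in expectation. The consequence is a diluted contrast and lost power.

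The size is unknown. At q = 20% the illustrations lose about 16 points (70% v 42%) and 19 points (60% v 35%), but these rest on assumed rates, an assumed q, and early refillers responding like everyone else. If they are persistent users, the recoverable loss could be only a few points. The direction, dilution toward no difference, rests only on some refills falling before randomization.

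**What to change.** In protocol 3.2(1) and 7.2.6 and in the SAP:

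- Start the pharmacy window at randomization, and state that the index fill and any other dispensing before randomization are excluded.
- Make the main measure any antipsychotic dispensing after randomization. This keeps the SAP's any-fill measure and gives it a start date.
- Keep refill as a separate measure only if it is defined as a dispensing of the initial drug, distinct from a switch.
- Add refill before randomization (yes/no), from the same pharmacy file, as a baseline covariate. It is fixed before assignment, so adjusting for it is legitimate, and it shows how large q was.

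This settles where the window starts. Where it ends is a separate matter: the SAP's eight weeks and H2's 6 months still have to be reconciled.

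The cost is amended wording and a few lines of programming on dispensing dates from pharmacy data already planned. It needs no new data collection, visits or participants, and should be settled before the antipsychotic data are analyzed by arm.
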